10.3 IMMUNE-RELATED ADVERSE EVENTS AS ADVERSE EVENTS OF SPECIAL INTEREST

Please see below in the Table 10.3: 1 regarding irAEs which must be reported as AESIs.

Table 10.3: 1 irAEs which must be reported as AESIs.

Immune-related adverse events of special interest
Pneumonitis (reported as an AESI if \geq Grade 2) 
• Acute interstitial pneumonitis• Interstitial lung disease• Pneumonitis
Colitis (reported as an AESI if \geq Grade 2 or any grade resulting in dose modification or use of systemic steroids to treat the AE) 
• Intestinal obstruction• Colitis• Colitis microscopic• Enterocolitis• Enterocolitis haemorrhagic• Gastrointestinal perforation• Necrotizing colitis• Diarrhea
Endocrine (reported as an AESI if \geq Grade 3 or \geq Grade 2 and resulting in dose modification or use of systemic steroids to treat the AE) 
• Adrenal insufficiency• Hyperthyroidism• Hypophysitis• Hypopituitarism• Hypothyroidism• Thyroid disorder• Thyroiditis• Hyperglycaemia, if \geq Grade 3 and associated with ketosis or metabolic acidosis
Endocrine (reported as an AESI) 
• Type 1 diabetes mellitus (if new onset)

Table 10.3: 1 irAEs which must be reported as AESIs.(cont'd)

Immune-related adverse events of special interest
Hematologic (reported as an AESI if \geq Grade 3 or any grade resulting in dose modification or use of systemic steroids to treat the AE)

• Autoimmune haemolytic anaemia• Aplastic anaemia• Thrombotic thrombocytopenic purpura• Idiopathic (or immune) thrombocytopenia purpura• Disseminated intravascular coagulation• Haemolytic-uraemic syndrome• Any Grade 4 anaemia regardless of underlying mechanism
Hepatic (reported as an AESI if \geq Grade 2, or any grade resulting in dose modification or use of systemic steroids to treat the AE)

• Hepatitis• Autoimmune hepatitis• Transaminase elevations (ALT and/or AST)
Infusion Reactions (reported as an AESI)

• Allergic reaction• Anaphylaxis• Cytokine release syndrome• Serum sickness• Infusion reactions• Infusion-like reactions
Neurologic (reported as an AESI)

• Autoimmune neuropathy• Guillain-Barre syndrome• Demyelinating polyneuropathy• Myasthenic syndrome
Ocular (report as an AESI if \geq Grade 2 or any grade resulting in dose modification or use of systemic steroids to treat the AE)

• Uveitis• Iritis

Table 10.3: 1 irAEs which must be reported as AESIs.(cont'd)

Immune-related adverse events of special interest
Renal (reported as an AESI if \geq Grade 2)

• Nephritis• Nephritis autoimmune• Renal failure• Renal failure acute• Creatinine elevations (report as an irAE if \geqGrade 3 or any grade resulting in dose modification or use of systemic steroids to treat the AE)
Skin (reported as an AESI)

• Dermatitis exfoliative• Erythema multiforme• Stevens-Johnson syndrome• Toxic epidermal necrolysis
Skin (reported as an AESI if \geq Grade 3)

• Pruritus• Rash• Rash generalized• Rash maculopapular• Any rash considered clinically significant in the physician's judgment
Other (reported as an AESI)

• Myocarditis• Pancreatitis• Pericarditis• Any other Grade 3 event that is considered immune-related by the physician

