Data pooled from the combination trials showed that 326 patients (90.8%) treated so far have been reported with at least 1 AE. The most common individual AE (by preferred term) has been hypertension (20.3%), followed by asthenia (17.5%), diarrhoea (17.3%), nausea (16.7%), fatigue (15.3%), decreased appetite (12.8%), peripheral oedema (12.3%), and vomiting (10.3%). Six patients (1.7%) have been reported with AEs requiring dose changes; 25 patients (7.0%) had an AE leading to treatment discontinuation. Hypertension (8.4%) has been the most frequently reported Grade 3 event. Adverse events of Grade 4 have been reported for 13 patients (3.6%); each Grade 4 AE has been reported for a single patient. There have been 22 patients (6.1%) with AEs resulting in death; sepsis and general physical health deterioration (3 patients each, 0.8%) as well as respiratory failure (2 patients, 0.6%) have been the only fatal AEs reported for more than 1 patient. Adverse events under the SMQ haemorrhages occurred in 28 patients (7.8%), with 4 patients (1.1%) presenting AEs of Grade 3 and 3 patients (0.8%) presenting a Grade 5 AE. There have been 59 patients (16.4%) reported with immune-related AEs according to investigator's judgement; 7 patients (1.9%) had Grade 3 AEs and 6 patients (1.7%) had Grade 4 AEs.

Laboratory values from all conducted trials did not show any event that met Hy's law criteria.

The pharmacokinetics, pharmacodynamics and immunogenicity of BI 836880 were investigated based on data from the monotherapy Phase I studies.

Maximum plasma concentrations were reached shortly after the end of infusion. BI 836880 plasma concentration remained around the maximum for up to 8 h and started to decline afterwards slowly. Cmax and AUC increased in a dose-proportional manner over the entire dose range. As expected for a nanobody, the clearance was low, resulting in a terminal half-

life of ~11 days. The volume of distribution was also low and in the range of the average blood volume. An accumulation ratio of 1.20 to 1.92 was observed, showing slight accumulation of BI 836880 after multiple dosing. No pharmacokinetic interaction between BI 836880 and ezabenlimab was detected as the PK parameter were comparable between administration alone and in combination.

For a more detailed description of the drug profile refer to the current Investigator's Brochures (IB).

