The latest list of “Always Serious AEs” can be found in the eDC system. These events should always be reported as SAEs as described above.

Adverse events of special interest (AESIs)

The term AESI relates to any specific AE that has been identified at the project level as being of particular concern for prospective safety monitoring and safety assessment within this trial, e.g. the potential for AEs based on knowledge from other compounds in the same class. AESIs need to be reported to the sponsor’s Pharmacovigilance Department within the same timeframe that applies to SAEs, please see above.

The following are considered as AESIs:

Dose Limiting Toxicities

All DLTs are considered to be AESIs, and must be reported as such. The definition of DLT is presented in [Section 5.2.6.1](#). DLTs are no longer applicable in Part 2 of the study, therefore are no longer AESIs in Part 2.

Persistent hypertension despite treatment

A hypertensive episode will be considered an AESI if:

- SBP \geq 140 mmHg or DBP \geq 90 mmHg which persists longer than 2 days despite either the initiation of antihypertensive agent(s) in a patient without prior history of hypertension, or the intensification / addition of new antihypertensive agents in a patient with prior history of hypertension.

Immune-related adverse events (irAE)

Although all irAEs are to be reported as AEs, only clinically important irAEs need to be reported as AESIs as defined by the sponsor in [Appendix 10.3](#). Non-clinically important irAEs, such as mild to moderate rash and hypothyroidism, for example, do not need to be reported as AESIs. If an Investigator determines that a severe irAE or other clinically significant irAE that is not included in [Appendix 10.3](#) is medically significant, the investigator may also report this irAE as an AESI.

Recommendations for the management of irAEs are presented in [Appendix 10.4](#).

Infusion-related reactions

All infusion-related reactions need to be reported as AESIs.

In the event of an infusion-related reaction \leq Grade 2, the infusion rate of BI 836880 or ezabenlimab may be decreased by 50% or interrupted until resolution of the event and re-initiated at 50% of the initial rate until completion of the infusion. In patients experiencing infusion related reactions \leq Grade 2, subsequent infusions may be administered at 50% of the initial rate.

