- For Grade 3 irAEs, ezabenlimab and BI 836880 has to be withheld, and treatment with high-dose corticosteroids (1-2mg/kg/d) is usually warranted. Upon improvement, steroids should be tapered over 4-6 weeks. Non-steroidal immunosuppressives (e.g. infliximab, mycophenolate mofetil) should be considered if no improvement or worsening occurs within the initial 48 to 72 hours. Upon recovery to grade 1 or less, and on corticosteroid \leq 10 mg per day, restarting of ezabenlimab and BI 836880 may be considered for selected irAEs, but caution is advised, in particular in patients with early-onset irAEs. Expert consultancy is recommended prior to restart of therapy.
- Most Grade 4 irAEs warrant permanent discontinuation of ezabenlimab and BI 836880.
- Restart of therapy is commonly possible for endocrine irAEs regardless of grade once stable hormone replacement has been instituted and symptoms have recovered. In case of multiple hormone deficiencies, corticosteroid replacement has to precede thyroid hormone replacement therapy by several days in order to avoid adrenal crisis.
- A dose reduction of BI 836880 may be considered, but is not required for the first occurrence of an endocrine irAE.

In case of prolonged steroid therapy or treatment with immunosuppressive consider the possibility of opportunistic infections and tuberculosis reactivation, administer prophylactic antibiotics where appropriate.

Commonly, referral to experts in the management of organ-specific conditions is highly recommended, especially for irAEs grade 3 or grade 4, or irAEs where management is complex.

Ezabenlimab and BI 836880 should be permanently discontinued for immune related:

- encephalitis, aseptic meningitis, transverse myelitis, or Guillain-Barre syndrome of any grade
- acquired thrombotic thrombocytopenic purpura of any grade
- myocarditis of any grade
- myasthenia gravis, peripheral neuropathy or autonomic neuropathy of grade ≥ 3
- myositis grade 2 with objective findings (see below), any myositis grade ≥ 3
- hepatitis grade ≥ 3 (transaminase >5 times ULN [or >10 times ULN if baseline was $>2.5-5$ times ULN] or total bilirubin >3 times ULN [or >5 times ULN if baseline was $>1.5-3$ times ULN], recurrent hepatitis grade ≥ 2)
- nephritis grade ≥ 3 , persisting grade 2 nephritis unresponsive to initial steroid therapy or worsening, and recurrent nephritis grade ≥ 2
- pneumonitis grade ≥ 3 ,

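### The catch-all entry of Table 10.3: 1 makes AESI reporting mandatory for unlisted Grade 3 immune-related events but, read literally, leaves unlisted Grade 4–5 events optional, mainly in Part 2

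*Protocol*

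**What the plan says.** Three places in the protocol settle which immune-related adverse events (irAEs) are AESIs.

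- **Section 5.2.7.1** limits the duty: "only clinically important irAEs need to be reported as AESIs as defined by the sponsor in" Appendix 10.3. It then adds a route for events outside that appendix: "If an Investigator determines that a severe irAE or other clinically significant irAE that is not included in" the appendix is medically significant, "the investigator may also report this irAE as an AESI".
- **Appendix 10.3** introduces Table 10.3: 1 with the words "regarding irAEs which must be reported as AESIs". The table is therefore the mandatory list. The last entry of its final category is "Any other Grade 3 event that is considered immune-related by the physician".
- **Section 5.2.6.1** makes every dose-limiting toxicity (DLT) in Part 1 an AESI. Section 5.2.7.1 states that this no longer applies in Part 2.

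AESI status has two practical effects in Section 5.2.7.2. SAEs and AESIs go to the sponsor on the SAE form within 24 hours. After the residual effect period (42 days from the last dose), only cancers of new histology, related SAEs and related AESIs are collected.

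**The concern.** A catch-all exists to pick up what the named rows miss. This one names Grade 3 alone. An unlisted immune-related event at Grade 3 is a mandatory AESI; at Grade 4 or 5 it is outside the table and falls to the discretionary wording of Section 5.2.7.1. The duty to report becomes weaker as the event becomes worse, and the protocol gives no reason for that.

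At stake is whether AESI data at the top grades are complete and comparable between sites, and whether a non-serious Grade 4 irAE reaches the sponsor promptly, or at all once the residual effect period is over.

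**Working it through.** No design figure depends on this point, so the check is a comparison of the rules.

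**1. Grade wording within Table 10.3: 1.** Eight category headings carry a grade threshold: pneumonitis, colitis, endocrine, hepatic, ocular and renal (each involving Grade 2 or Grade 3 as a minimum), and haematologic and skin (Grade 3 as a minimum). All eight use a greater-or-equal sign. Among single entries with their own grade, hyperglycaemia and creatinine also use the sign. Only Grade 4 anaemia and the catch-all do not.

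**2. Which events reach the catch-all.** Appendix 10.4 names as grounds for permanent discontinuation "encephalitis, aseptic meningitis, transverse myelitis, or Guillain-Barre syndrome of any grade". Of these four, only Guillain-Barré syndrome has an entry in Table 10.3: 1. Encephalitis, aseptic meningitis and transverse myelitis have none, and neither has myositis, which Appendix 10.4 also lists.

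**3. The rules applied to an unlisted event judged immune-related.**

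| Event | AESI in Part 1 | AESI in Part 2 | 24-hour report in any case? |
|---|---|---|---|
| Grade 3 | mandatory | mandatory | yes, as AESI |
| Grade 4, not serious | mandatory if it is a DLT, otherwise optional | optional | only if AESI |
| Grade 4, serious | mandatory if it is a DLT, otherwise optional | optional | yes, as SAE |
| Grade 5 | mandatory if it is a DLT, otherwise optional | optional | yes, as SAE |

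The DLT column rests on Table 5.2.6.1: 1, where drug-related non-haematologic Grade 4 or 5 events other than disease progression count as DLTs, subject to its exemptions. The row where the documents leave a real gap is the second.

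**4. Does that row contain anything?** Take a lipase rise judged immune-related and drug-related, without pancreatitis. Pancreatitis is a listed AESI; an isolated enzyme rise is not. At Grade 3 the rise is a mandatory AESI through the catch-all. At Grade 4 it is not in the table, Table 5.2.6.1: 1 exempts it from DLT status even in Part 1, and it need not meet any SAE criterion in Section 5.2.7.1. If it occurs after day 42, the Grade 3 case must be collected and the Grade 4 case need not be. One caution: lipase is not among the routine safety parameters of Section 5.2.3, so such a case would arise only from additional testing.

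**5. Scale.** Section 1.2.1 gives, for 359 patients in the pooled combination trials, "7 patients (1.9%) had Grade 3 AEs and 6 patients (1.7%) had Grade 4 AEs". The percentages reproduce: 7/359 = 1.9% and 6/359 = 1.7%. These counts cover all irAEs, listed and unlisted. The protocol does not say how many of the six Grade 4 patients had an event of an unlisted type, nor how many of those events were non-serious. Any number from none to six is compatible with the text.

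**The case against.** The strongest reply is that very little is lost.

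- **Serious events are covered.** Fatal and life-threatening events are SAEs, with the same form, the same 24-hour limit and the same collection after day 42 as AESIs. Grade 4–5 encephalitis, meningitis, myelitis or myositis would ordinarily qualify. This stands. These conditions show that the table is incomplete, but not that a report would be missed.
- **Other routes to AESI status exist.** The optional route of Section 5.2.7.1 and, in Part 1, the DLT rule both capture Grade 4–5 events. This stands in part. The first depends on the individual investigator. The second ends with Part 1, and Part 2 holds the large majority of patients (290 planned, against 12 to 18 evaluable in Part 1).
- **It is probably a missing symbol.** That is likely, and is an inference. Investigators still have to follow the text as printed.
- **It is late.** Recruitment stopped in December 2021, and 44 of 252 treated patients (44/252 = 17%) were still on treatment in January 2022. This limits the benefit for prospective reporting. It does not affect how AESIs are derived for the final report.

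A reader might go further and infer that the trial's immune-toxicity rate is biased low at the highest grades. The documents do not support that. Section 5.2.7.1 requires all irAEs to be reported as AEs, Section 5.2.7.2 collects all AEs through the residual effect period, and Section 7.3.4 tabulates frequency, severity and causality of all treatment-emergent AEs. The safety endpoints of Part 2 are AEs and drug-related AEs, not AESIs. A reader might also use the seven Grade 3 and six Grade 4 patients to size the loss. Those counts follow the investigator's judgement of immune-relatedness, not AESI status, include listed event types, and are not stated to be separate patients.

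**Conclusion.** The inconsistency is real and its reach is small. Read literally, the protocol requires AESI reporting of unlisted Grade 3 irAEs and leaves unlisted Grade 4–5 irAEs to discretion, mainly in Part 2. The effect is confined to two things: AESI classification at the top grades, which can vary between investigators, and non-serious unlisted Grade 4 irAEs, which can miss 24-hour reporting and, after day 42, collection altogether. The overall irAE rate through the residual effect period is not affected.

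The number of events concerned cannot be determined from the protocol. The conclusion assumes that the catch-all is applied as printed, and that the events in question are not on the sponsor's list of AEs always treated as serious, which is held in the eDC system and is not part of the protocol text.

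**What to change.** Reconcile the last entry of Table 10.3: 1 with the open-ended wording of the graded category headings and with Section 5.2.7.1, so that the mandatory reporting requirement does not weaken as grade rises. The simplest way is to make the entry open-ended, that is Grade 3 or higher. Section 5.2.7.1 can then keep its optional route for clinically significant irAEs below that grade.

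Apply the same rule when AESIs are derived from the AE data, using grade and the investigator's immune-related judgement, so that events already recorded are classified consistently whatever the site chose to report.

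This concerns safety reporting only and changes no dosing, discontinuation or treatment rule. The cost is one symbol in the table, the matching derivation, and a few extra AESI forms, most of them for events that will already be SAEs.

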10.4 MANAGEMENT OF IMMUNE-RELATED ADVERSE EVENTS

Regarding diagnosis, grading and therapeutic management of immune-related adverse events, grading and treatment, up-to-date published guidelines should be considered (e.g. [P19-00269](#)). Only limited guidance on management of specific irAEs can be given here.

Please refer to published guidelines (e.g. ASCO guideline, Brahmer (P19-00269)) for details.

In general,

- For irAEs listed below, it is not considered applicable stating that only if a causal relationship to one trial drug can be unequivocally established, the other trial drug may be continued. On combination treatment both drugs (BI 836880 and

Proprietary confidential information © 2023 Boehringer Ingelheim International GmbH or one or more of its affiliated companies

ezabenlimab) will be stopped, paused, or re-exposed together. Any exceptions to this have to be agreed with the sponsor.

- BI ezabenlimab and BI 836880 should be continued with close monitoring in case of grade 1 irAEs, with the exception of irAEs that may rapidly evolve into severe or fatal conditions (encephalitis of any grade, myocarditis of any grade, pneumonitis that is grade 1 but shows radiographic evidence of worsening – see detailed guidance below). A dose reduction of BI 836880 may be considered, but is not required for the first occurrence of an irAE grade 1.
- For most Grade 2 irAEs, ezabenlimab and BI 836880 should be withheld and treatment with corticosteroids is commonly warranted, usually with an initial dose of 0.5 to 1 mg/kg daily. Restart of therapy is commonly possible once symptoms and/or laboratory values have resolved to grade 1 or less, and on corticosteroid \leq 10 mg per day prednisone / prednisone equivalent per day. A dose reduction of BI 836880 should be considered, but is not required for the first occurrence of an irAE, but is mandatory if the same irAE recurs upon rechallenge with BI 836880.
- For Grade 3 irAEs, ezabenlimab and BI 836880 has to be withheld, and treatment with high-dose corticosteroids (1-2mg/kg/d) is usually warranted. Upon improvement, steroids should be tapered over 4-6 weeks. Non-steroidal immunosuppressives (e.g. infliximab, mycophenolate mofetil) should be considered if no improvement or worsening occurs within the initial 48 to 72 hours. Upon recovery to grade 1 or less, and on corticosteroid \leq 10 mg per day, restarting of ezabenlimab and BI 836880 may be considered for selected irAEs, but caution is advised, in particular in patients with early-onset irAEs. Expert consultancy is recommended prior to restart of therapy.
- Most Grade 4 irAEs warrant permanent discontinuation of ezabenlimab and BI 836880.
- Restart of therapy is commonly possible for endocrine irAEs regardless of grade once stable hormone replacement has been instituted and symptoms have recovered. In case of multiple hormone deficiencies, corticosteroid replacement has to precede thyroid hormone replacement therapy by several days in order to avoid adrenal crisis.
- A dose reduction of BI 836880 may be considered, but is not required for the first occurrence of an endocrine irAE.

In case of prolonged steroid therapy or treatment with immunosuppressive consider the possibility of opportunistic infections and tuberculosis reactivation, administer prophylactic antibiotics where appropriate.

Commonly, referral to experts in the management of organ-specific conditions is highly recommended, especially for irAEs grade 3 or grade 4, or irAEs where management is complex.

Ezabenlimab and BI 836880 should be permanently discontinued for immune related:

- encephalitis, aseptic meningitis, transverse myelitis, or Guillain-Barre syndrome of any grade
- acquired thrombotic thrombocytopenic purpura of any grade
- myocarditis of any grade
- myasthenia gravis, peripheral neuropathy or autonomic neuropathy of grade ≥ 3
- myositis grade 2 with objective findings (see below), any myositis grade ≥ 3
- hepatitis grade ≥ 3 (transaminase >5 times ULN [or >10 times ULN if baseline was $>2.5-5$ times ULN] or total bilirubin >3 times ULN [or >5 times ULN if baseline was $>1.5-3$ times ULN], recurrent hepatitis grade ≥ 2)
- nephritis grade ≥ 3 , persisting grade 2 nephritis unresponsive to initial steroid therapy or worsening, and recurrent nephritis grade ≥ 2
- pneumonitis grade ≥ 3 ,
- rash, bullous dermatoses, severe cutaneous adverse reaction, Stevens Johnson Syndrome, toxic epidermal necrolysis of grade 4, and recurrent rash grade ≥ 3
- colitis grade 4, and recurrent colitis of any grade
- uveitis, iritis, episcleritis of grade ≥ 3
- autoimmune-hemolytic anemia grade ≥ 2
- haemolytic uremic syndrome grade ≥ 3
- immune thrombocytopenia grade 4
- any recurrent irAE grade ≥ 3 ,
- inability to taper steroids to 10 mg or less prednisone or equivalent within 12 weeks, or persistent Grade 2-3 AEs that do not recover to Grade 1 or less within 12 weeks.

For BI 836880, up to 1 dose reductions are allowed if the treatment pause due to an AE. Dose adjustment of ezabenlimab besides interrupting of both compounds or permanently discontinuing ezabenlimab are not allowed (see [Section 4.1.4](#)).

Pneumonitis:

- For Grade 1 pneumonitis with radiographic evidence of worsening, withhold ezabenlimab and BI 836880 until improvement or resolution; ezabenlimab and BI 836880 may be reintroduced upon radiographic improvement. In the absence of radiographic improvement within 3-4 weeks, follow guidance as for grade 2 event.
- For Grade 2 pneumonitis, hold ezabenlimab and BI 836880 until resolution to at least grade 1. If not already started, initiate therapy for the event as per available guidelines. Follow guidance as for grade 3 pneumonitis if no clinical improvement after 48 -72 hr of starting therapy.
- For Grade 3-4 pneumonitis, permanently discontinue ezabenlimab and BI 836880 and immediately initiate treatment according to available guidelines.

Diarrhoea/Colitis:

- For Grade 1 diarrhoea/colitis, consider interruption of ezabenlimab and BI 836880 therapy.

Proprietary confidential information © 2023 Boehringer Ingelheim International GmbH or one or more of its affiliated companies

- For Grade 2 diarrhea/colitis, withhold ezabenlimab and BI 836880 until patient's symptoms recovered to grade 1 or less. Consider initiating treatment with steroids.
- For Grade 3 diarrhoea/colitis, withhold ezabenlimab and BI 836880 and immediately start treatment (steroids, non-steroidal immunosuppressants) as per available guidelines.
- For Grade 4 diarrhoea/colitis, permanently discontinue ezabenlimab and BI 836880 and immediately commence adequate therapy (e.g. i.v. corticosteroids).
- For Grade 1-3 colitis, restart of ezabenlimab and BI 836880 may be considered once symptoms improve to Grade 1 or less without need for continued steroids. After careful benefit risk assessment, ezabenlimab and BI 836880 may also be restarted after recovery to grade 1 or less, and on corticosteroid ≤ 10 mg per day
- Ezabenlimab and BI 836880 should be permanently discontinued for recurrent diarrhoea/colitis of any grade.

Diabetes

- Consider withholding ezabenlimab and BI 836880 in case of grade 2 hyperglycemia.
- Check for ketonuria. In case of new onset of diabetes or unexpected worsening of preexisting diabetes, check for new manifestation of type 1 diabetes.
- For new onset Type 1 diabetes mellitus, or Grade 3-4 hyperglycaemia associated with ketosis (ketonuria or metabolic acidosis)
 - Initiate insulin therapy
 - Evaluate subjects as appropriate per available guidelines regarding presence of type 1 diabetes
 - Ezabenlimab and BI 836880 should be withheld until glucose level is controlled with insulin with no sign of ketoacidosis.
- Ezabenlimab and BI 836880 may be restarted once insulin therapy has established stable glycemic control.

Thyroid disorders:

Thyroid disorders can occur at any time during treatment. Monitor subjects for changes in thyroid function (at screening and in regular intervals during treatment as indicated in [Flow Chart](#) (safety lab) and [Section 5.2.3](#), and as indicated based on clinical evaluation) and for clinical signs and symptoms of thyroid disorders. For diagnosed thyroid disorders, thyroid hormone supplementation and monitoring should occur as per available guidelines.

- Primary hypothyroidism:
 - For Grade 1 hypothyroidism, ezabenlimab and BI 836880 may be continued, with regular monitoring of thyroid values.
 - For Grade 2 hypothyroidism, consider withholding ezabenlimab and BI 836880
 - For Grade 3-4 hypothyroidism, withhold ezabenlimab and BI 836880, consider admission and IV therapy, especially in case of myxedema
 - Ezabenlimab and BI 836880 may be restarted once symptoms resolve to baseline with appropriate thyroid hormone supplementation

Proprietary confidential information © 2023 Boehringer Ingelheim International GmbH or one or more of its affiliated companies

- Primary hyperthyroidism:
 - For Grade 1 hyperthyroidism, ezabenlimab and BI 836880 may be continued, with regular monitoring of thyroid values.
 - For Grade 2 hyperthyroidism, consider withholding ezabenlimab and BI 836880, initiate therapy as per available guidelines.
 - For Grade 3-4 hyperthyroidism, withhold ezabenlimab and BI 836880. Consider hospitalization, especially in case of Thyrotoxicosis.
 - Ezabenlimab and BI 836880 may be restarted once symptoms resolve to baseline.
Note: in case of concomitant adrenal dysfunction, this must be corrected first, prior to thyroid hormone replacement (reduced stress tolerance)

Adrenal insufficiency

- Interruption of ezabenlimab and BI 836880 therapy should be considered for adrenal insufficiency grade 1 or 2, and is warranted for grade 3 and grade 4 adrenal insufficiency, until patient is stabilized on hormone replacement therapy.
- Therapy with ezabenlimab and BI 836880 may be restarted once stable replacement therapy has been achieved.
- Note: in case of concomitant hypothyroidism, steroid replacement therapy should precede thyroid hormone substitution to avoid adrenal crisis.

Hypophysitis

- Diagnostic workup for hypophysitis should be considered e.g. for patients with multiple endocrinopathies, unexplained fatigue, new severe headaches or vision changes.
- Patients should be appropriately advised regarding potentially reduced stress tolerance and increased substitution demands e.g. in case of infections, and to wear a medical alert bracelet to inform medical personnel about potentially increased hormone demands in situations of stress, in case of emergencies.
- Interruption of ezabenlimab and BI 836880 therapy should be considered for Grade 1 or 2 hypophysitis, and is warranted for Grade 3 and higher hypophysitis, until patient is stabilized on hormone replacement therapy.

Hepatitis

- Work-up for other causes of elevated liver enzymes, see also section on potential DILI ([Section 5.2.7](#)).
- For Grade 1 hepatitis (elevated AST/ALT $< 3 \times$ ULN and/or total bilirubin $< 1.5 \times$ ULN), ezabenlimab and BI 836880 may be continued, close monitoring of liver values is warranted.
- For Grade 2 hepatitis (AST/ALT 3–5 \times ULN and/or total bilirubin > 1.5 to $\leq 3 \times$ ULN), ezabenlimab and BI 836880 should be suspended. Monitoring of liver values every 3 days is recommended. Initiate treatment according to available guidelines. Restarting of ezabenlimab and 836880 may be considered upon recovery to grade 1 or less, and on corticosteroid ≤ 10 mg per day.
- For Grade 3 or higher hepatitis, ezabenlimab and BI 836880 has to be permanently discontinued. Immediately initiate treatment as per guidelines.

For eligible patients with elevated screening/baseline AST/ALT (>2.5-5x ULN or bilirubin >1.5-3x ULN):

- Carefully monitor patients for signs of autoimmune hepatitis.
- In case of increased levels of AST/ALT >2x baseline to ≤10x ULN and/or bilirubin >2x baseline to ≤5x ULN, ezabenlimab and BI 836880 should be suspended. Monitoring of liver values every 3 days or more frequently, if clinically indicated, is recommended. Restarting of ezabenlimab and BI 836880 may be considered upon recovery to baseline or less, and on corticosteroid ≤ 10 mg per day.
- In case of increased AST/ALT >10x ULN and/or bilirubin >5x ULN, ezabenlimab and BI 836880 have to be permanently discontinued. Initiate treatment as per guidelines.

Nephritis

- For Grade 1 nephritis, consider temporarily withholding ezabenlimab and BI 836880.
- For Grade 2 nephritis, withhold ezabenlimab and BI 836880. Consult nephrology. Initiate treatment according to guidelines. In case of no improvement or worsening, permanently discontinue ezabenlimab and BI 836880. Ezabenlimab and BI 836880 may only be re-started upon recovery to grade 1 or less, and on corticosteroid ≤ 10 mg per day.
- For Grade 3 or higher nephritis, permanently discontinue ezabenlimab and BI 836880. Consult nephrology. Treat with steroids 1-2 mg/kg prednisone or equivalent. If improved to grade 1 or less, taper corticosteroids over no less than 4-6 weeks.
- Ezabenlimab and BI 836880 should also be permanently discontinued for recurrent nephritis grade 2 or higher.

Rash

- For Grade 1 rash, continue ezabenlimab and BI 836880. Initiate topical treatment.
- For Grade 2 rash, ezabenlimab and BI 836880 may be continued, in case of no improvement upon weekly monitoring, consider interruption of ezabenlimab and BI 836880 therapy. Treat topically, add systemic therapies as clinically appropriate.
- For Grade 3 rash, withhold ezabenlimab and BI 836880. Initiate topical and systemic therapy as per available guidelines. Upon improvement of event to grade 1 or less, and on corticosteroid ≤ 10 mg per day, consult with dermatology whether therapy with ezabenlimab and BI 836880 might be restarted, especially in case no alternative anti-neoplastic therapy is available.
- For Grade 4 rash, ezabenlimab and BI 836880 should be permanently discontinued.
- Ezabenlimab and BI 836880 should also be discontinued for recurrent rash grade 3 or higher.

Bullous dermatosis

- For Grade 1 bullous dermatosis, use local wound care and observation. Ezabenlimab and BI 836880 can be continued.
- For Grade 2 bullous dermatosis, withhold ezabenlimab and BI 836880. Administer topical therapy, add systemic therapy as clinically adequate.

Proprietary confidential information © 2023 Boehringer Ingelheim International GmbH or one or more of its affiliated companies

- For Grade 3 bullous dermatosis, withhold ezabenlimab and BI 836880, initiate topical and systemic therapy as per available guidelines. Restarting of ezabenlimab and BI 836880 may be considered after dermatology consultation.
- For Grade 4 bullous dermatosis, permanently discontinue ezabenlimab and BI 836880.

Severe cutaneous adverse reaction (SCAR), Stevens Johnson Syndrome (SJS), Toxic Epidermal Necrolysis (TEN)

- For Grade 2 events, withhold ezabenlimab and BI 836880, initiate treatment as per available guidelines. Closely monitor for improvement or worsening.
- For Grade 3 events, withhold ezabelimab and BI 836880. Initiate treatment as per available guidelines. In case mucous membranes are affected, involve appropriate disciplines in management to prevent sequelae from scarring (e.g. ophthalmology).
- For Grade 4 events, permanently discontinue ezabenlimab and BI 836880, immediately administer adequate therapy. Immediate admission to burn center or intensive care with dermatology and wound care is recommended, involve appropriate other disciplines as needed in management of mucosal involvement.

In case of Grade 2 or Grade 3 events, ezabenlimab and BI 836880 may only be re-started upon event recovered to Grade 1 or less, on corticosteroid ≤ 10 mg per day, and after consultation with dermatology.

Encephalitis/Aseptic meningitis

- Ezabenlimab and BI 836880 should be permanently discontinued for any grade.

Myasthenia gravis

- For Grade 2 myasthenia gravis, withhold ezabenlimab and BI 836880.
- For Grade 3 or 4 myasthenia gravis, permanently discontinue ezabenzimab and BI 836880

Guillain Barré Syndrome (GBS)

- Discontinue ezabenlimab and BI 836880 permanently for any grade GBS.

Transverse Myelitis

- Discontinue ezabenlimab and BI 836880 permanently for any grade transverse myelitis.

Peripheral neuropathy, autonomic neuropathy

- For Grade 1 events, may continue ezabenlimab and BI 836880, but with low threshold to discontinue while monitoring closely for worsening.
- For Grade 2 events, withhold ezabenlimab and BI 836880 until resolution to grade 1 or less, and on corticosteroid ≤ 10 mg per day. Initiate therapy as appropriate per available guidelines.
- For Grade 3 or grade 4 events, permanently discontinue ezabenlimab and BI 836880.

Inflammatory Arthritis

Proprietary confidential information © 2023 Boehringer Ingelheim International GmbH or one or more of its affiliated companies

- For Grade 1 arthritis, ezabenlimab and BI 836880 can be continued. Administer analgetic treatment (acetaminophen, NSAID).
- For Grade 2-4 arthritis, withhold ezabenlimab and BI 836880. Initiate treatment as per available guidelines, care regarding reactivation of tuberculosis/opportunistic infections in case of prolonged immunosuppressive/disease modifying anti-rheumatic drugs DMARD therapy.

Ezabenlimab and BI 836880 may be restarted after consultancy with rheumatology once recovery to grade 1 or less, and on corticosteroid ≤ 10 mg per day.

Myositis

Diagnostic workup should consider the need to also evaluate myocardial involvement.

- For Grade 1 myositis, ezabenlimab and BI 836880 may be continued. Initiate adequate therapy as clinically warranted. In case of elevated CK or muscle weakness, treat as grade 2.
- For Grade 2 myositis, withhold ezabenlimab and BI 836880, discontinue permanently in patients with objective findings (elevated enzymes, abnormal EMG, abnormal muscle MRI or biopsy). Initiate therapy as per available guidelines. Resuming ezabenlimab and BI 836880 may be considered in patients without objective findings, symptoms have resolved to grade 1 or less without any immunosuppressive therapy, and after consultation with rheumatology/neurology.
- For Grade 3 or 4 myositis, permanently discontinue ezabenlimab and BI 836880.
- Ezabenlimab and BI 836880 should be permanently discontinued if there is any evidence of myocardial involvement.

Polymyalgia-like syndrome

- For Grade 1 event, ezabenlimab and BI 836880 can be continued.
- For Grade 2 event, withhold ezabenlimab and BI 836880 and promptly initiate adequate therapy. If no improvement, treat as grade 3.
- For Grade 3 or Grade 4 event, withhold ezabenlimab and BI 836880, promptly initiate adequate therapy. Rheumatology consultancy is highly recommended.

Ezabenlimab and BI 836880 may be resumed after careful assessment of risks and benefits, rheumatology consultancy highly recommended prior to reinitiation. Ezabenlimab and BI 836880 may only be re-started upon recovery to grade 1 or less and on corticosteroid ≤ 10 mg per day.

Myocarditis

- Discontinue ezabenlimab and BI 836880 permanently for any grade of myocarditis.

Uveitis/Iritis, Episcleritis

- For Grade 1 events, treatment with ezabenlimab and BI 836880 can continue. Treat topically as needed.
- For Grade 2 events, withhold therapy with ezabenlimab and BI 836880, urgent ophthalmology referral is recommended. Initiate topical treatment, consider systemic therapy if needed. Restart of ezabenlimab and BI 836880 is permitted once resolved to grade 1 or less, and off systemic steroids (for the ocular condition, if steroids needed for other irAEs, up to 10 mg prednisone or equivalent are permitted). Continuation of

Proprietary confidential information © 2023 Boehringer Ingelheim International GmbH or one or more of its affiliated companies

topical/ocular steroids is permitted and does not prohibit resuming ezabenlimab and BI 836880 therapy.

- For Grade 3 or 4 events, permanently discontinue ezabenlimab and BI 836880 therapy. Seek emergent ophthalmology consultation. Initiate adequate local and systemic treatment.

Autoimmune-hemolytic anemia (AIHA)

- For Grade 1 AIHA, continue treatment with ezabenlimab and BI 836880. Close follow-up of anemia and other lab values.
- For Grade 2-4 AIHA, discontinue ezabenlimab and BI 836880 permanently. Initiate systemic therapy as per guideline. Consult Hematology.

Acquired thrombotic thrombocytopenic purpura (TTP), haemolytic uremic syndrome.

Timely recognition upon suggestive findings is essential, timely/immediate involvement of hematology consultancy may be beneficial.

- For any grade TTP, permanently discontinue ezabenlimab and BI 836880.
- For HUS (TTP excluded), withhold ezabenlimab and BI 836880 for grade 1 and grade 2, provide supportive care. Upon full recovery, ezabenlimab and BI 836880 may be restarted after carefully weighing of risks and benefits.
- For Grade 3 or Grade 4 HUS, discontinue ezabenlimab and BI 836880 permanently.

Immune thrombocytopenia (ITP)

- In case of Grade 1 ITP, ezabenlimab and BI 836880 can be continued.
